8.2.4.6. Infrequent Tier 1 Adverse Events of Special Interest

Infrequent Tier 1 adverse events of special interest will be defined as those included in the following categories:

- Breast cancer
- Potential for decreased male fertility due to effects on sperm/semen characteristics
- Interference with formation of external genitalia in a male fetus if a woman carrying a male fetus is exposed to dutasteride

- Hair changes
- Allergic reactions
- Depressed mood
- Testicular pain and swelling
- Intraoperative floppy iris syndrome
- Orthostasis
- Priapism
- Stevens-Johnson syndrome
- Atrial fibrillation, tachycardia, arrhythmias

MedDRA preferred terms and codes included in these special interest adverse events are defined in [Appendix 8, Table D](#). Total number of infrequent Tier 1 events as well as the number and percentage of subjects with infrequent Tier 1 events will be provided by treatment group.

Listings of infrequent Tier 1 adverse events of special interest will be provided.

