For computing AE duration, partial AE start and end dates will be imputed as previously described, and events with completely unknown (missing) end dates will be censored at the latter of the following two dates: date of last clinic visit, latest AE start date. AE duration is the total number of non-overlapping days for all events per subject, and will be considered censored if any contributing event is censored.

Time to death is defined as (date of death – treatment start date +1). For subjects who do not experience death, time to death is censored at the date of last clinic visit (if missing,

the subject will be censored at the treatment start date).

Special interest adverse events, including MedDRA preferred terms and codes, are presented below in [Table A](#)-[Table D](#):

Table A: Sexual and Breast Adverse Events of Special Interest

Table B: Prostate Cancer Adverse Events of Special Interest

Table C: Cardiovascular Adverse Events of Special Interest

Table D: Infrequent Tier 1 Adverse Events of Special Interest

Table A. Sexual and Breast Adverse Events of Special Interest: MedDRA Preferred Terms and Codes		
Special Interest Event	MedDRA Preferred Term	PT_Code
Altered (Decreased) Libido	Sexual dysfunction	10040477
	Male sexual dysfunction	10057672
	Libido decreased	10024419
	Loss of libido	10024870
	Libido disorder	10061221
Impotence	Erectile dysfunction	10061461
	Organic erectile dysfunction	10052004
	Disturbance in sexual arousal	10058929
	Psychogenic erectile dysfunction	10052005
Ejaculation Disorders	Ejaculation delayed	10014325
	Ejaculation disorder	10014326
	Ejaculation failure	10014328
	Retrograde ejaculation	10038967
	Anorgasmia	10002652
	Orgasm abnormal	10031085
	Premature ejaculation	10036596
	Male orgasmic disorder	10025513
	Orgasmic sensation decreased	10052449
	Semen volume decreased	10039944
Breast Disorders	Breast hyperplasia	10006256
	Breast enlargement	10006242
	Gynaecomastia	10018800
	Nipple disorder	10029417
	Breast engorgement	10006240
	Breast swelling	10006312
	Breast pain	10006298
	Breast tenderness	10006313
	Nipple pain	10029421
	Nipple swelling	10058680
Breast Disorders: Breast Enlargement	Breast discomfort	10049872
	Breast hyperplasia	10006256
	Breast enlargement	10006242
	Gynaecomastia	10018800
	Nipple disorder	10029417
	Breast engorgement	10006240
Breast Disorders: Breast Tenderness	Breast swelling	10006312
	Breast pain	10006298
	Breast tenderness	10006313
	Nipple pain	10029421
	Nipple swelling	10058680

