	Coronary artery occlusion	10011086
	Coronary artery stenosis	10011089
	Coronary artery thrombosis	10011091
	Myocardial ischemia	10028600
	Coronary artery disease	10011078
	Arteriosclerosis coronary artery	10003211
Cardiac Arrhythmias	Ventricular extrasystoles	10047289
	Torsade de Pointes	10044066
	Ventricular fibrillation	10047290
	Cardiac Fibrillation	10061592
	Pulseless electrical activity	10058151
	Ventricular asystole	10047284
	Long QT syndrome	10024803
	Ventricular tachycardia	10047302
	Ventricular Arrhythmia	10047281
	Ventricular flutter	10047294
Peripheral Vascular Disease	Deep Vein Thrombosis	10051055

Table D. Infrequent Tier 1 Adverse Events of Special Interest: MedDRA Preferred Terms and Codes

Special Interest Event	MedDRA Preferred Term	PT_Code
Relevant for dutasteride:		
Allergic reactions	Anaphylactic reaction	10002198
	Anaphylactic shock	10002199
	Anaphylactic transfusion reaction	10067113
	Anaphylactoid reaction	10002216
	Anaphylactoid shock	10063119
	Circulatory collapse	10009192
	Kounis syndrome	10069167
	Shock	10040560
	Type I hypersensitivity	10045240
	Allergic oedema	10060934
	Angioedema	10002424
	Circumoral oedema	10052250
	Conjunctival oedema	10010726
	Corneal oedema	10011033
	Epiglottic oedema	10015029
	Eye oedema	10052139
	Eye swelling	10015967
	Eyelid oedema	10015993
	Face oedema	10016029
	Gingival oedema	10049305
	Gingival swelling	10018291
	Gleich's syndrome	10066837
	Hereditary angioedema	10019860
	Idiopathic angioedema	10073257
	Idiopathic urticaria	10021247
	Laryngeal oedema	10023845
	Laryngotracheal oedema	10023893
	Limbal swelling	10070492
	Lip oedema	10024558
	Lip swelling	10024570
	Mouth Swelling	10075203
	Oculorespiratory syndrome	10067317
	Oedema mouth	10030110
	Oropharyngeal swelling	10031118
	Palatal oedema	10056998
	Palatal swelling	10074403
	Periorbital oedema	10034545
	Pharyngeal oedema	10034829
	Scleral oedema	10057431
	Swelling face	10042682
	Swollen tongue	10042727
	Tongue oedema	10043967
	Tracheal oedema	10044296
	Urticaria	10046735
	Urticaria cholinergic	10046740
	Urticaria chronic	10052568
	Urticaria papular	10046750
	Acquired epidermolysis bullosa	10056508
	Blister	10005191
	Blister rupture	10073385

Table D. Infrequent Tier 1 Adverse Events of Special Interest: MedDRA Preferred Terms and Codes

Special Interest Event	MedDRA Preferred Term	PT_Code
	Bullous impetigo	10006563
	Conjunctivitis	10010741
	Corneal exfoliation	10064489
	Drug eruption	10013687
	Epidermolysis	10053177

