	HER-2 positive breast cancer	10065430
	Inflammatory carcinoma of breast recurrent	10021977
	Inflammatory carcinoma of breast stage III	10021978
	Inflammatory carcinoma of breast stage IV	10021979
	Inflammatory carcinoma of the breast	10021980
	Intraductal papillary breast neoplasm	10073540
	Intraductal proliferative breast lesion	10073094
	Invasive ductal breast carcinoma	10073095
	Invasive lobular breast carcinoma	10073096
	Invasive papillary breast carcinoma	10073098
	Lobular breast carcinoma in situ	10073099
	Malignant nipple neoplasm	10062051
	Malignant nipple neoplasm female	10053129
	Malignant nipple neoplasm male	10053128
	Mastectomy	10026878
	Medullary carcinoma of breast	10027095
	Metaplastic breast carcinoma	10073100
	Modified radical mastectomy	10027799
	Mucinous breast carcinoma	10073101
	Neuroendocrine breast tumour	10073103
	Oestrogen receptor assay positive	10054054
	Oestrogen receptor positive breast cancer	10070577
	Page's disease of nipple	10033364
	Photon radiation therapy to breast	10034949
	Postmastectomy lymphoedema syndrome	10036390

Table D. Infrequent Tier 1 Adverse Events of Special Interest: MedDRA Preferred Terms and Codes

Special Interest Event	MedDRA Preferred Term	PT_Code
	Progesterone receptor assay positive	10054057
	Radical mastectomy	10037773
	Radiotherapy to breast	10062090
	Simple mastectomy	10040700
	Tubular breast carcinoma	10073104
	X-ray therapy to breast	10048199
	Antioestrogen therapy	10002816
	Breast reconstruction	10006305
	Breast neoplasm	10006279
	Nipple neoplasm	10056286
	Phyllodes tumour	10071776
	Biopsy breast abnormal	10004745
	Breast calcifications	10048782
	Breast dysplasia	10006237
	Breast prosthesis implantation	10006303
	Computerised tomogram breast abnormal	10074534
Depressed mood	Activation syndrome	10066817
	Adjustment disorder with depressed mood	10001297
	Columbia suicide severity rating scale abnormal	10075616
	Adjustment disorder with mixed anxiety and depressed mood	10001299
	Agitated depression	10001496
	Anhedonia	10002511
	Antidepressant therapy	10054976
	Childhood depression	10068631
	Decreased interest	10011971
	Depressed mood	10012374
	Depression	10012378
	Depression postoperative	10012390
	Depressive symptom	10054089
	Dysphoria	10013954
	Electroconvulsive therapy	10014404
	Feeling guilty	10049708
	Feeling of despair	10016344
	Feelings of worthlessness	10016374
	Major depression	10057840
	Menopausal depression	10067371
	Post stroke depression	10070606
	Postictal depression	10071324

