	Perinatal depression	10078366
	Completed suicide	10010144
	Depression suicidal	10012397
	Intentional overdose	10022523
	Intentional self-injury	10022524
	Poisoning deliberate	10036000
	Self-injurious ideation	10051154
	Suicidal behaviour	10065604
	Suicidal ideation	10042458
	Suicide attempt	10042464

Table D. Infrequent Tier 1 Adverse Events of Special Interest: MedDRA Preferred Terms and Codes

Special Interest Event	MedDRA Preferred Term	PT_Code
Hair changes	Alopecia	10001760
	Alopecia areata	10001761
	Alopecia scarring	10001764
	Alopecia syphilitic	10001765
	Alopecia totalis	10001766
	Alopecia universalis	10001767
	Hypotrichosis	10021126
	Progeria	10036794
	Madarosis	10051235
	Follicular mucinosis	10056506
	Application site alopecia	10059046
	Androgenetic alopecia	10068168
	Satoyoshi syndrome	10070579
	Radiation alopecia	10072045
	Diffuse alopecia	10073736
	Hypertrichosis	10020864
Interference with formation of external genitalia in a male fetus	Congenital vas deferens absence	10010670
	Cryptorchism	10011498
	Epispadias	10015088
	Hypospadias	10021093
	Reproductive tract hypoplasia, male	10057858
	Testicular dysplasia	10059271
	Congenital genital malformation male	10059492
	Penoscrotal fusion	10064951
	Sertoli-cell-only syndrome	10066833
	Buried penis syndrome	10067131
	Penoscrotal transposition	10067287
	Penile torsion	10070235
Potential for decreased male fertility	Infertility tests	10021931
	pH semen	10034784
	pH semen decreased	10034786
	pH semen increased	10034788
	pH semen normal	10034790
	Red blood cells semen	10038176
	Red blood cells semen negative	10038179
	Red blood cells semen positive	10038180
	Semen liquefaction	10039931
	Semen liquefaction normal	10039933
	Semen liquefaction prolonged	10039934
	Semen liquefaction shortened	10039935
	Semen viscosity	10039936
	Semen viscosity decreased	10039938
	Semen viscosity increased	10039940
	Semen viscosity normal	10039942
	Semen volume abnormal	10039943
	Semen volume decreased	10039944
	Semen volume increased	10039946
	Semen volume normal	10039948
	Sperm analysis	10041476
	Sperm analysis abnormal	10041477
	Sperm analysis normal	10041478
	Spermatozoa abnormal	10041498
	Spermatozoa morphology	10041501

Table D. Infrequent Tier 1 Adverse Events of Special Interest: MedDRA Preferred Terms and Codes

Special Interest Event	MedDRA Preferred Term	PT_Code
Testicular pain and swelling	Spermatozoa morphology abnormal	10041502
	Spermatozoa morphology normal	10041503

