	Spermatozoa progressive motility abnormal	10041504
	Spermatozoa progressive motility decreased	10041506
	Spermatozoa progressive motility normal	10041507
	White blood cells semen	10047956
	White blood cells semen negative	10047959
	White blood cells semen positive	10047960
	Fructose semen decreased	10052476
	Fructose semen increased	10052477
	Prostatic fluid leukocytes increased	10053866
	Infertility tests abnormal	10062020
	Infertility tests normal	10062021
	pH semen abnormal	10062074
	Semen liquefaction abnormal	10062159
	Semen viscosity abnormal	10062160
	Semen analysis normal	10062238
	Semen analysis	10068482
	Semen analysis abnormal	10068483
	Sperm concentration decreased	10070925
	Sperm concentration increased	10070926
	Sperm concentration abnormal	10070927
	Sperm concentration normal	10070928
	Sperm concentration	10070929
	Sperm concentration zero	10070930
	Total sperm count	10070931
	Total sperm count decreased	10070932
	Infertility	10021926
	Infertility male	10021929
	Anorchism	10002641
	Eunuchoidism	10015532
	Hypogonadism male	10021011
	Testicular atrophy	10043298
	Testicular disorder	10043306
	Testicular failure	10043315
	Testicular failure postoperative	10043317
	Testicular failure primary	10043318
	Testicular hyperfunction	10043334
	Testicular infarction	10043337
	Testicular pain	10043345
	Testicular retraction	10043348
	Testicular swelling	10043354
	Testicular torsion	10043356
	Testicular necrosis	10049572
	Spermatic cord mass	10049792
	Testicular appendage torsion	10050476
	Spermatic cord pain	10051221
	Testicular injury	10051872
	Testicular haemorrhage	10051877
	Epididymal calculus	10052321
	Epididymal enlargement	10052322
	Epididymal tenderness	10052323
	Testis discomfort	10052531

Table D. Infrequent Tier 1 Adverse Events of Special Interest: MedDRA Preferred Terms and Codes

Special Interest Event	MedDRA Preferred Term	PT_Code
	Monorchidism	10055002
	Epididymal disorder	10055045
	Spermatic cord disorder	10056348
	Testicular mass	10058901
	Testotoxicosis	10063654
	Spermatic cord haemorrhage	10065742
	Spermatic cord obstruction	10065805
	Spermatic cord perforation	10065806
	Spermatic cord stenosis	10065807
	Testicular perforation	10065808
	Testicular hypertrophy	10066101
	Testicular oedema	10066769
	Sperm granuloma	10067802
	Testicular microlithiasis	10067829
	Congenital monorchidism	10069505
	Testicular autoimmunity	10071574
Relevant for tamsulosin:		
Atrial fibrillation, tachycardia, arrhythmias	Arrhythmia	10003119

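### The Peripheral Vascular Disease category holds only deep vein thrombosis, so its table and plot are mislabelled and peripheral arterial events drop out of the cardiovascular total; the Table D lists could also misclassify

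*SAP*

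**What the plan says.** The current text is RAP Amendment 01. Section 8.2.4.2 describes Tier 1 events of special interest as preferred terms specified in advance because a treatment effect is hypothesised for them. Membership of a category is fixed by code list. Section 8.2.4.6 states that the "MedDRA preferred terms and codes included in these special interest adverse events are defined in" Appendix 8 Table D, and Section 8.2.4.5 points to Table C in the same way for cardiovascular events.

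**Cardiovascular (Table C).** Section 8.2.4.5 names six categories, one of them peripheral vascular disease. Each is summarised separately, all are pooled into one further category, and Kaplan-Meier estimates are planned. For Peripheral Vascular Disease, Table C lists one term: "Deep Vein Thrombosis". It feeds Table 3.61, Figure 3.16 and, through the pooled category, Table 3.62.

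**Infrequent Tier 1 (Table D).** Section 8.2.4.6 includes a category described as "Potential for decreased male fertility due to effects on sperm/semen characteristics". Its list contains "Sperm analysis normal" and "Semen analysis normal" among other normal or negative results. The Breast Cancer list contains "Simple mastectomy" and "Antioestrogen therapy" with no condition on why they were done or given. "Gynaecomastia" is a separate special-interest term in Table A. The planned output for these categories is the number of events and the number and percentage of subjects by arm, in Table 3.63.

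**The concern.** Because the code list is the definition, a category can be no better than its list.

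For peripheral vascular disease the label and the content do not match. A reader of Table 3.61 or Figure 3.16 would take the result as covering peripheral arterial disease, and a low or equal count as reassurance about it, although no such event could have been counted. The gap carries into the pooled cardiovascular category, which is the figure most likely to be quoted.

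For Table D the risk runs the other way: a record that describes no harm, or a different harm, could be counted. A normal semen result reported as an adverse event would add to a category meant to show impaired fertility. Breast surgery or an anti-oestrogen recorded for a reason other than cancer would add to Breast Cancer. If the reason were breast enlargement, such records might be unevenly spread between arms.

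**Working it through.** No sample size, power or event figure bears on this point. The check is a count of the lists and a trace to the outputs.

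**Table C, terms per category.** Acute coronary syndrome 9, ischemic cerebrovascular 26, cardiac failure 11, ischemic coronary 7, cardiac arrhythmias 10, peripheral vascular disease 1. Total 9 + 26 + 11 + 7 + 10 + 1 = 64. The arterial terms among the other 63 concern coronary, cerebral, carotid or vertebral arteries. None is a peripheral arterial event. The December 2015 RAP has the same single-term entry, and item 08 of Appendix 17 confines its revisions to Table D.

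**Trace to output.**
- Deep vein thrombosis: in Table 3.61, Figure 3.16 and Table 3.62.
- Peripheral arterial event: in none of these. It appears only in the general adverse event tables, such as Table 3.2.
- The listing that maps verbatim to preferred terms (Section 8.2.4.2) covers terms already in the special-interest categories, so it would not show an omitted event.

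**Table D, fertility.** The list runs from Infertility tests to Infertility male. At a page break in the amended version the next category's label sits too high; the 2015 version shows that the sperm and semen terms beside it belong to fertility.
- All terms: 54
- Ending in normal or negative: 12 (12/54 = 22%)
- Test name with no result: 11 (11/54 = 20%)
- Remainder, describing an abnormality: 54 − 12 − 11 = 31
- List after deleting the 12: 54 − 12 = 42

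**Table D, breast cancer.**
- All terms: 60
- Treatments, procedures or their sequelae (mastectomy and breast radiotherapy terms, anti-oestrogen therapy, reconstruction, prosthesis implantation, post-mastectomy lymphoedema): 14 (14/60 = 23%)
- Two receptor assays, abnormal biopsy, abnormal CT, calcifications, dysplasia: 6
- Together: 14 + 6 = 20 (20/60 = 33%)
- Remainder: 60 − 20 = 40. These still include names that do not state malignancy, such as breast neoplasm, nipple neoplasm, phyllodes tumour and intraductal proliferative breast lesion.

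**Comparison within the SAP.** Table B defines prostate cancer by eight terms, all of them diagnoses, with no surgery, biopsy or assay term. Breast cancer is built on the opposite principle.

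**Routes into the count.** Table D is applied to recorded post-randomization adverse events. The schedule in Appendix 2 has no semen test. Concomitant drugs are logged separately (Section 6.5). The documents give no event frequencies, so no corrected count can be computed.

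**The case against.** **On Table C.** Deep vein thrombosis is a vascular event, so the term is not misplaced. A peripheral arterial event would still appear in the overall adverse event tables. The definitions come from the PSAP, whose reasons are not shown. All of this stands, but none of it repairs the label or restores the missing events to the pooled total. The separate cardiovascular data collection mentioned in Section 8.2.4.5 goes to listings, not into these categories.

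**On Table D.** The case against is strong. A listed term is not a counted event: a normal semen test enters only if an investigator reports it as an adverse event, and none is scheduled. The lists read as broad search lists, with terms that can hardly occur in male subjects (Breast cancer female, Menopausal depression). Table 3.63 is a MedDRA-level display, and Listings 3.11 and 3.12 would let a reader recognise a mastectomy record for what it is. No treatment test or Kaplan-Meier analysis is specified for this group. These arguments reduce the point to a minor one. What remains is that no rule takes such a record out of the reported subject count.

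**Stronger readings.** A reader might infer that the fertility and breast cancer counts are wrong, or that 23 of 54 terms (43%) is a miscount rate. The documents support neither: the percentages are shares of dictionary entries, not of events. Nor does it follow that the fertility row could not show impairment, since 31 of its terms describe an abnormality. That breast cancer would be inflated in the combination arm needs a chain of events: more breast enlargement there, treated by surgery or an anti-oestrogen, and that treatment coded as an adverse event. The SAP does not mention such treatment for gynaecomastia, so this is a possibility only.

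**Conclusion.** The Peripheral Vascular Disease definition is wrong as written. One venous term stands under a broader label, and peripheral arterial events are absent from Table 3.61, Figure 3.16 and the all-cardiovascular Table 3.62. This rests only on the contents of Table C and the output list, not on any assumption about the data. How many events would be affected is unknown.

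The Table D point holds in a weaker form: the lists could misclassify, because nothing excludes normal results or checks the indication. Its effect on the counts cannot be quantified and may be nil. It depends on such terms being recorded as adverse events, which the documents neither plan for nor rule out.

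**What to change.** **Table C, before unblinding, one of two:**
- rename the category, Table 3.61 and Figure 3.16 to deep vein thrombosis, and state in Section 8.2.4.5 that peripheral arterial events are not in the cardiovascular total; or
- add the peripheral arterial preferred terms to Table C, chosen with the safety coding group under the MedDRA version in use.

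**Table D, minor:**
- delete the 12 normal or negative terms from the fertility list;
- show the 20 breast procedure, treatment, assay and non-malignant finding terms on a separate review row, and count a subject under Breast Cancer only with a malignant or in-situ diagnosis. State the rule by diagnosis, because moving the 20 terms alone would leave names that do not specify malignancy.

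Record each change as a departure from the PSAP, as Section 8.2 provides. Amendment 01 already edited the Table D terms, so there is precedent. The cost is edits to two code-list tables, two titles if the category is renamed, and one extra row. Term-for-term comparability with PSAP-based reports falls slightly; the review row preserves it for the breast terms.

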11.9. Appendix 9: Threshold Factors for Clinical Laboratory Tests and Vital Signs

Hematology and Clinical Chemistry Laboratory Tests, Codes and Threshold Factors				
LABORATORY TEST	Database LBTESTCD	Unit	Multiplicative Factors ¹	
			Low (x LLN)	High (x ULN)
HEMATOLOGY				
-Hemoglobin	HB_BLC	G/L	0.75	-
-Platelet count	PLT_BLC	GL/L	0.75	1.5
-WBC count	WBC_BLC	GL/L	0.5	3.0
-RBC count	RBC_BLC	GL/L	0.5	-
CLINICAL CHEMISTRY				
-Albumin	ALB_PLA	G/L	0.9	1.2
-ALT	ALT_PLA	IU/L	-	3.0
-Alkaline Phosphatase	ALP_PLA	IU/L	-	1.5
- AST	AST_PLA	IU/L	-	3.0
-Creatinine	CRT_PLA	UMOL/L	0.5	3.0
-Glucose	GLUC_PLA	MMOL/L	0.7	1.75
-Potassium	K_PLA	MMOL/L	0.75	1.4
-Sodium	NA_PLA	MMOL/L	0.9	1.15
-Total Bilirubin	BILT_PLA	UMOL/L	-	2.5
-Total Protein	TP_PLA	G/L	0.8	1.15
-Urea/BUN	UREA_PLA	MMOL/L	0.5	2.0
1. A laboratory value that is above the upper limit factor multiplied by the upper limit of the normal range is considered a high threshold value. A laboratory value that is below the lower limit factor multiplied by the lower limit of the normal range is considered a low threshold value.				

Threshold Ranges for Vital Signs			
		Threshold Ranges	
Vital Sign	Unit	Lower	Upper
Systolic Blood Pressure	mmHg	<80	>165
Diastolic Blood Pressure	mmHg	<40	>105
Heart Rate	bpm	<40	>100

11.10. Appendix 10: Examination of Covariates and Subgroups

Endpoint(s)	IPSS change from baseline
Analysis	Subgroup Summaries and General Linear Model

A list of subgroups of interest for the primary efficacy endpoint is below. If the categorization defining the subgroups results in overly sparse data or if some baseline subgroups are homogeneous in response, then particular subgroups may be combined or not reported.

For each subgroup, IPSS change from baseline summaries will be output by treatment group at Month 12 and at Month 24 for the ITT population using both LOCF and At Visit approaches. No statistical comparisons will be performed.

The effects of baseline subgroups and their interactions with treatment will be assessed. As a minimum, these subgroups will include those in the below table except for country and center. These effects will be individually explored in terms of: 1) addition of subgroup effect to the model* and 2) addition of subgroup effect and subgroup effect by treatment interaction to the model*.

*Refers to primary efficacy General Linear Model (GLM):

Change from Baseline IPSS = treatment + cluster + baseline IPSS.

In these analyses, continuous variables will be treated as continuous and not as dichotomous subgroups. These assessments will focus on Month 24 LOCF, and separately Month 24 At Visit, and will be output as listings. Other analyses based on other time points will not be output unless substantive finding dictate.

Subgroups Summarized for Primary Efficacy Endpoint	
Subgroup	Categorization for Tabular Summary Display
Baseline Age 65	<65, ≥65 years
Baseline Age 75	<75, ≥75 years
Baseline IPSS	<20, ≥20
Baseline BPH-Related Health Status	<4, ≥4
Baseline Prostate Volume	<40, ≥40cc
Baseline Qmax	<10, ≥10ml/sec
Alpha Blocker History	Yes, No
5-Alpha-Reductase Inhibitor History	Yes, No
Phytotherapy History	Yes, No
Alpha Blocker or 5-Alpha-Reductase Inhibitor History	Yes, No
Alpha Blocker or 5-Alpha-Reductase Inhibitor or Phytotherapy History	Yes, No
Baseline PSA	<3, ≥3ng/ml
Country (cluster)	China, Japan, Korea, Taiwan
Center	Each center with at least one randomized subject.

